## **6 STUDY DRUG**

### **6.1 Investigational Medicinal Product**

The study medication is Olumacostat Glasaretil Gel, 5.0%.

Olumacostat Glasaretil Gel is formulated as an alcohol based gel for topical application. Olumacostat Glasaretil Gel, 5.0% contains 50 mg of Olumacostat Glasaretil per gram of gel, ethanol, isopropanol, polyethylene glycol 400, dimethyl isosorbide and hydroxypropyl-cellulose and appears as a translucent, colorless to faintly yellow gel.

### **6.2 Packaging, Labeling and Storage**

Olumacostat Glasaretil Gel, 5.0% will be packaged in 45g aluminum tubes. Each tube contains approximately 40g of gel.

Study drug tubes will be labeled with the study number, a unique tube number, contents, storage conditions, manufacturer and Sponsor information, precautionary statements and expiry date if applicable.

Study drug tubes are to be stored at room temperature (25°C with allowable excursion to 15-30°C) in a secure, locked facility accessible only to authorized study personnel. Study drug must not be placed in refrigerator or frozen, exposed to heat or stored at high temperatures. This product is flammable. Avoid fire, flame, or smoking during and immediately following application.

### **6.3 Treatment Assignment**

Subjects will maintain the unique subject number assigned at randomization into their study of origin (either DRM01B-ACN03 or DRM01B-ACN04). All subjects will receive Olumacostat Glasaretil Gel, 5.0%, BID.

### **6.4 Study Blinding**

This is an open-label study. Subjects will not be unblinded to their treatment assignment prior to enrollment into this study (DRM01B-ACN05). Once enrolled, each subject will receive Olumacostat Glasaretil Gel, 5.0%.

### **6.5 Study Drug Dispensing and Return**

It is the responsibility of the Investigator to ensure that study drug is only used on study subjects enrolled in this study. The study drug must only be dispensed from official study sites by authorized personnel according to the protocol and local regulations.

Study drug will be dispensed by the study site to the subject at each study visit. Two tubes contain enough study drug for 1 month of application. At each visit, the subject will be dispensed enough tubes to allow dosing until the next visit. Partially used tubes may be re-dispensed at the site's discretion.

Subjects are to return all study medication tubes (used and unused) to the study site. Study tubes will be weighed prior to dispensing and upon return, and if required, prior to re-dispensing. Weights will be recorded in the source documents and eCRF.

Each subject is to be instructed on the importance of returning study drug at the next study visit. If a subject does not return study drug, they will be instructed to return it as soon as possible. The site staff will visually inspect the tube to ensure product usage is consistent with the subject's dosing diary.

### **6.6 Study Drug Application**

Subjects will apply the study drug twice daily (morning and evening) to a clean, dry face. Subjects will be re-instructed on the application of the study drug, if needed.

Study drug is to be applied topically, to the entire face (forehead, nose, cheeks, and chin) by squeezing approximately ½ inch or 1.3 centimeter long line of gel onto a finger and spreading the gel over the face, avoiding the skin around the eyes, eyelids and mouth, until the face is completely covered.

For subjects originating in the DRM01B-ACN03 study, subjects may continue to apply study drug may all affected areas on the trunk (i.e., chest, shoulders and back) by spreading a thin layer of gel over the entire affected areas.

Subjects originating in DRM01B-ACN04 should continue to apply study drug to the face only.

Subjects will be instructed to wash their hands prior to and immediately following study drug application.

Subjects should avoid washing the face or swimming within 2 hours of applying study medication. Missed doses should be applied, provided there is an 8-hour window until the next scheduled dose.

### **6.7 Treatment Compliance**

Treatment compliance will be assessed at each visit using a subject-completed diary and visual inspection of the tubes. Subjects will be given a paper diary at each visit in conjunction with study medication. The subject-completed diary will collect application information for the face, chest, back and shoulders. Subjects will be instructed to bring all study medication and diaries to the clinic at the next study visit.

A subject deviating significantly from the assigned dosing regimen on the face, will be counseled. All diaries will be maintained as source documentation.

The first and last dates of study product usage, location and any missed applications will be recorded in the eCRF.

### **6.8 Study Drug Accountability**

The Investigator or designee will be responsible for study drug accountability and records at the site. Study drug accountability records will document the receipt, dispensing and return of study drug and provide a complete account of all used and unused drug product. Study drug accountability records will be reviewed regularly throughout the study by the Sponsor/designee. Study drug will be returned to the Sponsor, or designee, at the end of the study, following final study drug accountability.

## **7 CONCOMITANT MEDICATIONS AND PROCEDURES**

All medications (including over-the-counter drugs, vitamins, antacids and skin care products) taken throughout the study will be recorded on the eCRF.

Medication entries should be specific to the generic name (if a combination drug, then marketed product name) and will include the dose, unit, frequency, route of administration, start date, discontinuation date, and indication. When listing medications indicated for acne, the area treated will be collected.

The Investigator should examine the acceptability of all concomitant procedures, medications, topical preparations and dietary supplements not explicitly prohibited in this study. In order to ensure that appropriate concomitant therapy is administered, subjects will be instructed to consult with the Investigator prior to taking any medication (either self-administered non-prescription drugs or prescription therapy prescribed by another physician).

### **7.1 Permitted Treatments and Procedures**

The use of concomitant medications for medical conditions (e.g., hypertension, diabetes, acute infections) or treatment of an adverse event is permitted during this study as long as medications are not explicitly prohibited by the protocol.

Non-medicated moisturizers and make-up may be used during study participation, provided application occurs after study medication is applied. On study visit days, non-medicated moisturizers and make-up must be removed prior to each study visit as instructed by the Investigator. Subjects' skin care regimen should remain stable/unchanged during study participation.

Non-medicated moisturizers, soaps, and make-up do not need to be recorded as concomitant medications.

### **7.2 Prohibited Treatments and Procedures**

Subjects should not undergo any elective medical procedure without prior consultation with the Investigator. Elective out-patient procedures (e.g., minor outpatient surgery) that might require hospitalization or anesthesia should be deferred until after the study, whenever clinically appropriate. However, subjects may continue in the study if not contraindicated by the procedure or if continuation is not deemed in the subject's best interest.

The following medications and treatments are prohibited during the study:

- Over-the-counter topical medications for acne vulgaris including benzoyl peroxide, topical anti-inflammatory medications, corticosteroids,  $\alpha$ -hydroxy/glycolic acid
  - With the following exception: Subjects originating in DRM01B-ACN04 may apply non-systemically-absorbing over-the-counter topical medications for acne vulgaris on truncal acne if warranted by the Investigator
- Systemically absorbed anti-acne drugs
- Systemic corticosteroids (use of intranasal and inhaled corticosteroids allowed for seasonal allergies and asthma)
- Systemic antibiotics (except in the case of acute medical need to treat infections)
- Prescription topical retinoid use (e.g., tretinoin, tazarotene, adapalene)
- New hormonal therapy or dose change to existing hormonal therapy. Hormonal therapies include, but are not limited to, estrogenic and progestational agents such as birth control pills.

- Use of androgen receptor blockers (such as spironolactone or flutamide)
- Oral retinoid use (e.g., isotretinoin) or vitamin A supplements greater than 10,000 units/day
- Facial procedures (chemical or laser peel, microdermabrasion, etc.)
- Sun exposure which in the opinion of the investigator could affect the course of acne or any tanning booth use

## **8 STUDY PROCEDURES**

The procedures required for subject evaluation at each study visit are outlined below and in the study Schedule of Visits and Procedures (see [Appendix 1](#)). The timing of each study day is relative to the day of initial dosing (Baseline/Day 1). Visit windows are provided to allow study sites some flexibility in maintaining the study visit schedule for participating subjects. Out of window visits may be unavoidable in certain circumstances. Out of window visits are not considered deviations to the protocol.

### **8.1 Day 1 (Week 12 Visit of DRM01B-ACN03 or DRM01B-ACN04 Study)**

- Obtain written informed consent/assent. For subjects under legal adult age, both parents or legal representatives may be required to sign informed consent as applicable.
- Assess Inclusion/Exclusion criteria
- Dispense study drug and diary
- Schedule next visit

The following Week 12 data collected as part of the DRM01-ACN03 or DRM01-ACN04 study will be used for the Day 1 visit:

- Query subject for concomitant medication use
- Perform a complete physical examination
- Record weight
- Measure pulse and blood pressure
- Collect a 12-lead ECG
- Conduct Investigator Global Assessment
- Collect Acne Patient Self-Questionnaire
- Draw blood samples for laboratory tests and urine for urinalysis. Include serum pregnancy test for women of childbearing potential
- Assess Local Skin Reactions (LSR)
- Review and record AEs
- Collect photographs (selected sites)

**8.2 Week 2 Telephone Contact (+/-2 days)**

- Call subject to review AEs and concomitant medications
- Schedule next visit

**8.3 Weeks 4, 8, 16, 20, 28 and 32 (+/-4 days)**

- Collect concomitant medication information
- Collect urine pregnancy for women of childbearing potential
- Measure pulse and blood pressure
- Review and record AEs
- Assess LSRs
- Perform symptom-directed physical exam
- Review compliance/Weigh tubes and dispense drug and diary
- Schedule next visit

**8.4 Week 12 and 24 (+/-4 days)**

- Collect concomitant medication information
- Collect urine pregnancy for women of childbearing potential
- Measure pulse and blood pressure
- Review and record AEs
- Assess LSRs
- Conduct Investigator's Global Assessment and assess subject's eligibility to continue treatment.
- Collect Acne Patient Self-Questionnaire
- Collect photographs at Week 12 only (selected sites)
- Perform symptom-directed physical exam
- Review compliance/Weigh tubes and dispense drug and diary
- Schedule next visit

**8.5 Week 36 (+/-4 day) Study Exit or Early Termination Visit**

- Collect concomitant medication information
- Measure pulse and blood pressure
- Review and record AEs
- Conduct a complete physical exam

- Measure weight and height
- Collect a 12 lead ECG
- Draw blood samples for laboratory tests. Include serum pregnancy test for women of childbearing potential. Include urinalysis if clinically indicated
- Assess LSRs
- Conduct Investigator Global Assessment
- Collect Acne Patient Self-Questionnaire
- Collect photographs (selected sites)
- Review compliance/Weigh tubes and collect all study medication and diary

## 8.6 **Unscheduled Visits**

Additional visits may be scheduled as necessary to ensure the safety and well-being of subjects who experience AEs. Laboratory evaluations, if necessary, will be collected and analyzed using the central laboratory for this study. Data will be recorded in the eCRF. If an immediate result is required to adequately care for a subject, a duplicate sample may be submitted to a local lab.

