### **9.4.3 ECGs**

12-lead ECG measurements will be obtained for all subjects at the Day 1 and Week 36 Study Exit or Early Termination visits. The subject should rest quietly for at least 5 minutes in a supine position prior to ECG collection. The ECG should be obtained either prior to the time of blood collection, or at least 15 minutes afterwards.

All study sites will be supplied with standardized, validated digital 12-lead ECG (12 lead at 25 mm/sec reporting rhythm, ventricular rate, the RR interval, the PR interval, QRS duration, QT and QTcF intervals) equipment capable of recording, storing, and printing producing high resolution 12-lead ECG data by the central laboratory. Study sites will be trained on the use of the equipment prior to study start.

Machine-read ECG recordings will be collected and analyzed centrally. Data will be transferred electronically to the database.

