### **9.4.4 Laboratory Evaluations**

Laboratory tests will be collected to evaluate safety in all study subjects and analyzed using a central laboratory. Labs will be collected per the Schedule of Visits and Procedures (see [Appendix 1](#)) or more frequently as clinically indicated. Laboratory samples are to be shipped on the same day as collected. No more than 4 mL/kg total will be collected over an 8-week period in subjects under legal adult age. Laboratory tests are described below.

Hematology: hematocrit, hemoglobin, red blood cell (RBC) count, white blood cell count and differential (%), mean corpuscular hemoglobin (MCH), mean corpuscular hemoglobin concentration (MCHC), mean corpuscular volume, RBC morphology, platelet count, absolute

neutrophils, absolute lymphocytes, absolute monocytes, absolute eosinophils, and absolute basophils.

Chemistry: sodium, potassium, chloride, calcium, phosphorus, bicarbonate, uric acid, blood urea nitrogen (BUN), creatinine, total protein, albumin, aspartate aminotransferase (AST), alanine aminotransferase (ALT), alkaline phosphatase, bilirubin (total and direct), and glucose (fasting or non-fasting).

Serum pregnancy testing will be performed at Baseline/Day 1 and Week 36 Study Exit or Early Termination visits. Urine pregnancy testing (beta human chorionic gonadotropin [ $\beta$ -hCG]) will be performed at Weeks 4 – 36 visits for all females unless post-menopausal/sterile.

Urinalysis: pH, specific gravity, protein, glucose, ketones, bilirubin, blood, nitrite, urobilinogen, leukocyte esterase. A microscopic examination of urine will be performed if clinically indicated (e.g. a positive dipstick for protein, blood, leukocyte esterase) in the opinion of the Investigator based on the findings of the urinalysis or clinical signs and symptoms. Any new or worsened clinically significant laboratory result is to be recorded as an AE after study drug dosing.

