**15 APPENDIX 1 – SCHEDULE OF VISITS AND PROCEDURES**

Visit	Day 1	Week 2 (phone call) (+/- 2 days)	Week 4, 8, 16, 20, 28, 32 (+/- 4 days)	Weeks 12, 24 (+/- 4 days)	Week 36 Study Exit/ Early Term. (+/- 4 days)
Informed Consent/Assent	X				
Inclusion/Exclusion Criteria	X				
Complete Physical Exam, Weight, Height	X b				X
Symptom-directed Physical Exam			X	X	
Pulse and Blood Pressure	X		X	X	X
Adverse Events	X	X	X	X	X
Local Skin Reactions	X b		X	X	X
Concomitant Medications	X	X	X	X	X
Safety labs: Serum Chemistry, Hematology, Serum Pregnancy, Urinalysis	X b				X
Urine Pregnancy Test			X	X	
Photographs a	X b			X c	X
12-Lead ECGs	X b				X
Dispense Study Medication/Diary	X		X	X	
Investigator Global Assessment	X b			X	X
Acne Patient Self-Questionnaire	X b			X	X
Study Medication Compliance			X	X	X

a Selected sites only

b Week 12 data collected as part of the DRM01-ACN03 or DRM01-ACN04 study will be used for the Day 1 visit

c Week 12 only

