**ACN05 Nominal Visit Windows for Efficacy and Safety Assessments**

Nominal Visit	Target Study Day	Window (Days)
Week 4	29	22 to 42
Week 8	57	43 to 70
Week 12	85	71 to 98
Week 16	113	99 to 126
Week 20	141	127 to 154
Week 24	169	155 to 182
Week 28	197	183 to 210
Week 32	225	211 to 238
Week 36	253	239 to 266

Data collected at ET and unscheduled visits prior to study day 22 will not be analyzed. Data collected at ET and unscheduled visits after study day 266 will not be included in analyses.

The definition for the study day included in each study window is defined as below:

$$\text{Study Day prior to Day 1} = \text{Visit Date} - \text{Day 1 Date}$$

$$\text{Study Day on or after Day 1} = \text{Visit Date} - \text{Day 1 Date} + 1$$

If an assessment's mapped nominal visit is a visit at which the subject has data from a scheduled visit present, or if no analyses are planned for the assessment at the mapped nominal visit, the data collected at the ET or unscheduled visit will not be included in analyses.

In the event of multiple values from unscheduled or ET assessments within a nominal visit window, the value closest to the scheduled visit target study day will be used for analyses. If two values tie as closest to the time point (for example, one value is before and the other value is after the time point), then the later value will be selected.

Other data summaries will include information collected at ET visits as Week 36/ET.

Data collected at all visits will be included in the data listings with the ACN05 analysis visit presented.

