### **6.8.3      Clinical Laboratory Evaluation**

Laboratory data will be presented in a by-subject listing. Any clinically significant laboratory abnormalities will be captured as adverse events. Changes from Baseline in safety laboratory values will be summarized at the final follow-up evaluation using descriptive statistics for the safety population in total, as well as by treatment received in ACN03/ACN04. For subjects receiving Olumacostat Glasaretil Gel, 5.0% in ACN03/ACN04, the final follow-up analysis visit will be Week 48/ET. For subjects receiving Olumacostat Glasaretil Gel, Vehicle in ACN03/ACN04, the final follow-up analysis visit will be Week 36/ET.

Additionally, changes from Baseline in safety laboratory values will be summarized using shift tables according to normal ranges.

If repeat laboratory testing was performed to follow-up on original results, summaries will be based on original results for each visit. If repeat laboratory testing was performed due to unavailable original test results (e.g., poor sample quality, insufficient amounts, etc.) summaries will be based on repeat results for each visit.

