### **6.8.4      Other Observations Related to Safety**

#### **6.8.4.1      ECG Measurements**

ECG data will be summarized at the final follow-up evaluation using descriptive statistics for the safety population in total, as well as by treatment received in ACN03/ACN04. Descriptive statistics will be provided for the following ECG parameters, for observed values and changes

from Baseline: heart rate (HR), RR duration, QRS duration, PR duration, QT duration and QTc duration. Change from Baseline in ECG abnormalities will also be summarized using shift tables at the final evaluation visit.

Shift tables will be based on the following categories:

- PR Interval: < 100 msec, 100 – 220 msec and > 220 msec;
- QRS Interval: < 50 msec, 50 – 110 msec and > 110 msec;
- QTcF Interval: < 450 msec, 450 – 500 msec and > 500 msec.

For subjects receiving Olumacostat Glasaretil Gel, 5.0% in ACN03/ACN04, the final follow-up analysis visit will be Week 48/ET. For subjects receiving Olumacostat Glasaretil Gel, Vehicle in ACN03/ACN04, the final follow-up analysis visit will be Week 36/ET.

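### Laboratory values from unscheduled visits, and any ECG taken at one, stay out of the laboratory and ECG tables, so a transient out-of-range value can be tabulated as normal to normal

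*Protocol*

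**What the plan says.** **Collection.** The row "Safety labs: Serum Chemistry, Hematology, Serum Pregnancy, Urinalysis" in Protocol Appendix 1 is marked only at Day 1 and at Week 36/ET. For ECGs, Protocol 9.4.3 says "12-lead ECG measurements will be obtained for all subjects at the Day 1 and Week 36 Study Exit or Early Termination visits". Between those points, Protocol 9.4.4 allows laboratory tests "or more frequently as clinically indicated". Protocol 8.6 allows extra visits for subjects with AEs, at which "Laboratory evaluations, if necessary, will be collected and analyzed using the central laboratory for this study", with the data entered in the eCRF. Neither 8.6 nor 9.4.4 mentions ECGs.

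**Mapping.** SAP 6.1.3 assigns unscheduled and ET data to visit windows for vital signs and LSRs; laboratory tests and ECGs are not named. Unscheduled and ET data before study day 22 or after day 266 are left out. If the mapped visit already has a scheduled value, or has no analysis planned for that assessment, "the data collected at the ET or unscheduled visit will not be included in analyses". For everything else, "Other data summaries will include information collected at ET visits as Week 36/ET"; unscheduled visits are not mentioned there. Listings include all visits.

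**Tables.** SAP 6.8.3: "Changes from Baseline in safety laboratory values will be summarized at the final follow-up evaluation using descriptive statistics". The laboratory shift table in the same section is by normal range and names no visit. SAP 6.8.4.1: "ECG data will be summarized at the final follow-up evaluation using descriptive statistics", and its shift table is tied to the final evaluation visit. Final follow-up is Week 48/ET for subjects who had 5.0% gel in ACN03/ACN04 (prior-active below) and Week 36/ET for those who had vehicle (prior-vehicle). SAP 6.8.4.4 plans a worst post-baseline grade for each LSR. Nothing equivalent is planned for laboratory tests or ECGs.

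**Import.** For prior-active subjects, SAP 6.1 brings in Weeks 4, 8 and 12 for LSRs and vital signs, but Baseline only for laboratory tests and ECGs.

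**The concern.** Long-term safety is the only objective of this study. A laboratory sample taken between Day 1 and exit is taken because someone had a clinical reason to take it, so these are the samples most likely to be abnormal. The plan collects and stores them but does not tabulate them. A subject whose liver enzyme rises on treatment and settles by exit would be counted in the same cell as a subject whose enzyme never moved. The laboratory and ECG tables would then describe the end of treatment, when a reader may take them to describe the whole of it.

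**Working it through.** The plan states no figure on this point, so there is nothing to reproduce. The check follows one unscheduled laboratory or ECG value through the SAP rules, for each ACN05 study day from 2 to 252, the day before the Week 36 target (day 253).

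1. **Narrow reading: only vital signs and LSRs are windowed.** The value has no analysis visit, and only ET visits are folded into Week 36/ET. Excluded on 251 of 251 days.

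2. **Wide reading: the window table applies to every safety assessment.**
   - Days 2 to 21, before the day-22 cut-off: 21 − 2 + 1 = 20 days, excluded.
   - Days 22 to 238, mapped to Weeks 4 to 32, where no laboratory or ECG analysis is planned: 238 − 22 + 1 = 217 days, excluded.
   - Days 239 to 252, mapped to Week 36: 252 − 239 + 1 = 14 days. Excluded if a scheduled Week 36 value exists; usable if not.
   - Total: 20 + 217 + 14 = 251 days. With a scheduled Week 36 value, 251 of 251 are excluded. Without one, 237 of 251 = 94.4%.

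   The result barely depends on the reading.

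3. **Extra samples at a scheduled clinic visit.** A test added at, say, Week 8 under Protocol 9.4.4 maps to that nominal visit, where SAP 6.8.3 plans no laboratory change summary. It is not tabulated there either.

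4. **Period covered by one tabulated follow-up value.**
   - Prior-active: the baseline is the ACN03/ACN04 baseline (SAP 6.1.2) and the final visit is Week 48/ET. 12 + 36 = 48 weeks; 48 × 7 = 336 days. Week 12 laboratory tests and ECG exist, because Protocol 8.1 and 9.1 carry them over as Day 1 data, and they were taken on 5.0% gel. SAP 6.1 does not import them, and they are not this group's baseline.
   - Prior-vehicle: 36 weeks; 36 × 7 = 252 days.

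5. **What reaches the tables.** Take a subject with normal baseline, an out-of-range value in between, and normal final value. The final-visit shift table records normal to normal. A worst-value table records a shift.

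6. **Illustration only.** The documents give no rate of such subjects; 0.5% to 5% is an assumption. Expected count = N × rate:

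| Assumed share | N = 700 | N = 100 | Final-visit shift table |
|---|---|---|---|
| 0.5% | 3.5 | 0.5 | 0 |
| 1% | 7 | 1 | 0 |
| 2% | 14 | 2 | 0 |
| 5% | 35 | 5 | 0 |

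700 is the approximate enrolment. 100 is the number treated for 36 weeks at which the study may stop. The zeros follow from the rules, whatever the rate.

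**The case against.** The strongest reply is that safety information does not depend on these tables. New or worsened clinically significant laboratory results must be recorded as AEs (Protocol 9.4.4 and 9.4.7, SAP 6.8.3). They then appear in the TEAE tables by SOC, preferred term, severity, relationship and 12-week onset period, which gives timing that a worst-value shift table would not. Subjects seen under Protocol 8.6 already have an AE, and every value is listed. This stands in large part. A reader might infer that unscheduled values vanish from every summary; the documents do not support that. What is lost is the value and the range shift, mainly for results not judged clinically significant. A coded term gives neither, and a listing gives no count or percentage.

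Three other strong readings also fail.

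- **Unscheduled ECGs.** A reader might picture a long QTcF found at an unscheduled visit. The protocol provides only for laboratory tests there, so the ECG part is conditional: if an ECG is taken, the SAP keeps it out. The AE safeguard is then less explicit, because Protocol 9.4.3 has no rule on recording significant ECG findings, although the general AE definition in 9.4.6 would cover them.
- **Laboratory shift table.** It cannot be said that the SAP expressly excludes unscheduled values from this table, because it names no visit. Final follow-up is the natural reading, and the silence itself needs correcting.
- **Vital signs.** The same criticism might be extended to pulse and blood pressure. These are measured at every clinic visit, four weeks apart, and unscheduled values are used when the window has no scheduled one. Clinically significant changes are AEs. Preferring the scheduled value in a by-visit table is ordinary practice.

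**Conclusion.** The point holds for numeric and shift information on laboratory tests and, conditionally, ECGs. Unscheduled values do not enter the laboratory change summaries, the ECG summaries or the ECG shift table. On the natural reading they do not enter the laboratory shift table. The one exception, under the wide reading, is a value from day 239 on in a subject with no scheduled Week 36 value. The single tabulated follow-up covers about 48 weeks for prior-active and 36 weeks for prior-vehicle subjects.

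The masking needs normal baseline and normal final values. An abnormality still present at exit or at the ET visit appears as a shift. How many subjects would be affected cannot be estimated from the documents, and the counts above are not evidence of a rate. This is an inexpensive improvement that should be made. It does not invalidate the safety analysis. The sentence in Protocol 8.6 is sound as it stands; the gap is in SAP 6.1, 6.1.3, 6.8.3 and 6.8.4.1.

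**What to change.** - **SAP 6.8.3 and 6.8.4.1:** add shift tables from Baseline to the worst post-baseline value: highest and lowest for laboratory tests, longest for PR, QRS and QTcF. Use all values after the first 5.0% application, whether scheduled, ET or unscheduled. Keep the final-visit tables.
- **SAP 6.1:** add the ACN03/ACN04 on-drug laboratory and ECG values of prior-active subjects, Week 12 at least, to the import list. Without them, the worst-value table would take in sporadic triggered values and omit a systematic on-drug one.
- **SAP 6.1.3:** state that the window and selection rules, including the study-day cut-offs, apply to by-visit tables only.
- **SAP 6.8.3:** name the visit used for the existing laboratory shift table.

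The cost is SAP wording, an import of data already collected, and one extra table set. There are no new visits or samples. The downside is that event-triggered values show whether an abnormality occurred, not how common it was at a time point; a footnote should say so.
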